#### **Exploratory endpoint:**

For exploratory objective, we will assess the effects of Polyphenon E on the grade of cirrhosis, as measured by FibroScan. We will also develop an LC-MS and/or ELISA-based method for detecting urinary and blood  $\gamma$ -OHPdG. Additionally, we will measure the incidence of HCC across all dosage levels.

Descriptive statistics (n; min; max; mean; median; SD for continuous variables; and n, frequency for categorical variables) will be used to summarize participant demographics. Participant safety data will be tabulated according to the symptom and grade. Estimates will be presented with their 95% confidence intervals.

Proposed Sample Size: Final number of n=2 to 48 subjects.

Proposed Sample Size: A minimum of 4 and maximum of 171 eligible cirrhotic participants will be screened. Enrollment of subjects will stop according to the dose escalation 3 + 3 design, plus an expansion cohort of up to 24 subjects at the maximum tolerated dose if one is established, for a total of n = 2 to 48 subjects.

### **13.6 Reporting and Exclusions**

We expect that we will identify an MTD from the 3+3 dose escalation cohort, then move to dose expansion cohort.

We expect that 2 to 48 subjects will have complete data on the primary endpoint. Main analysis will be based on the complete data. Additional descriptive analysis may be performed to see if dropouts show a systematic property. Thus, we expect the 15% of data missing values will be studied to determine possible patterns and dependence with other relevant variables.

We will report the reasons for any missing outcomes to determine if they may be related to the unobserved outcome. We will write a cautionary note that results could be biased if there is a background change in  $\gamma$ -OHPdG over time that is unrelated to Polyphenon E treatment.

### **13.7 Evaluation of Toxicity**

All participants will be evaluable for toxicity from the time of their first dose.

### **13.8 Evaluation of Response**

*Intent to treat analysis:* All samples from all subjects who receive drug will be evaluated and included in the primary analysis, which will be based on intent to treat principle.

### **13.9 Interim Analysis**

In dose escalation cohort, subjects enrolled in each dose level will be monitored for liver toxicities for four weeks prior to enrolling additional participants in the next dose level.

Since all study subjects are planned to be enrolled within 12 months, interim analysis for efficacy will not be performed.

### **13.10 Ancillary Studies**

The distribution of  $\gamma$ -OHPdG in participants with cirrhosis and stability of  $\gamma$ -OHPdG in cirrhotic participants have been studied, and data is provided in section 2.3.4 and 2.3.5 on page 13.

## **14. ETHICAL AND REGULATORY CONSIDERATIONS**

### **14.1 Form FDA 1572**

Prior to initiating this study, the Protocol Lead Investigator at the Lead or Participating Organization(s) will provide a signed Form FDA 1572 stating that the study will be conducted in compliance with regulations for clinical investigations and listing the investigators, at each site that will participate in the protocol. All personnel directly involved in the performance of procedures required by the protocol and the collection of data should be listed on Form FDA 1572.

### **14.2 Other Required Documents**

14.2.1 Current (within two years) CV or biosketch for all study personnel listed on the Form FDA 1572 and Delegation of Tasks form for the Lead Organization and all Participating Organizations. CVs or biosketches do not need to be updated for participating study staff after drug shipment authorization (DSA).

14.2.2 Current medical licenses (where applicable) for all study personnel listed on Form FDA 1572 and Delegation of Tasks form for the Lead Organization and all Participating Organizations.

14.2.3 Lab certification (e.g., CLIA, CAP) and lab normal ranges for all labs listed on Form FDA 1572 for the Lead Organization and all Participating Organizations.

14.2.4 Documentation of Good Clinical Practice training for all study personnel listed on the FDA Form 1572 and Delegation of Tasks form for the Lead Organization and all Participating Organizations.

14.2.5 Documentation of Federalwide Assurance (FWA) number for the Lead Organization and all Participating Organizations.

14.2.6 Signed Investigator's Brochure/Package Insert acknowledgement form

14.2.7 Delegation of Tasks form for the Lead Organization and all Participating Organizations signed by the Principal Investigator for each site and initialed by all study personnel listed on the form

14.2.8 Signed and dated NCI, DCP Financial Disclosure Form for all study personnel listed on Form FDA 1572 for the Lead Organization and all Participating Organizations

### **14.3 Institutional Review Board Approval**

Prior to initiating the study and receiving agent, the Investigators at the Lead Organization and the Participating Organization(s) must obtain written approval to conduct the study from the appropriate IRB. Should changes to the study become necessary, protocol amendments will be submitted to the DCP PIO according to DCP Amendment Guidelines. The DCP-approved amended protocol must be approved by the IRB prior to implementation

### **14.4 Informed Consent**

All potential study participants will be given a copy of the IRB-approved Informed Consent to review. The investigator will explain all aspects of the study in lay language and answer all questions regarding the study. If the participant decides to participate in the study, he/she will be asked to sign and date the Informed Consent document. The study agent(s) will not be released to a participant who has not signed the Informed Consent document. Subjects who refuse to participate or who withdraw from the study will be treated without prejudice.

Participants must be provided the option to allow the use of blood samples, other body fluids, and tissues obtained during testing, operative procedures, or other standard medical practices for further research purposes. If applicable, statement of this option may be included within the informed consent document or may be provided as an addendum to the consent. A Model Consent Form for Use of Tissue for Research is available through a link in the DCP website.

Prior to study initiation, the informed consent document must be reviewed and approved by NCI, DCP, the Consortium Lead Organization, and the IRB at each Organization at which the protocol will be implemented. Any subsequent changes to the informed consent must be approved by NCI, DCP, the Consortium Lead Organization's IRB, and then submitted to each organization's IRB for approval prior to initiation.

#### **14.6 Other**

This trial will be conducted in compliance with the protocol, Good Clinical Practice (GCP), and the applicable regulatory requirements.

### **15. FINANCING, EXPENSES, AND/OR INSURANCE**

Study subjects will be provided with a compensation as follows:

- \$200 for each liver biopsy (at Screen 2 and at Visit 3)
- \$75 for each clinic visit, for transportation, parking, childcare, etc. (Screen 1, Screen 2, Visit 1, Visit 2, Visit 3, and Visit 4).
- \$25 for each weekly/bi-weekly blood draw between visits (max of 14). Participants will be provided \$25 for the blood draw even if it is performed at an outside clinic.

The maximum total provided to each participant, depending on the requirements of their participation, is \$1,200.

**APPENDIX A**  
**Performance Status Criteria**

**ECOG Performance Status Scale**

| Grade | Descriptions   |
|--------------|---|
| 0            | Normal activity. Fully active, able to carry on all pre-disease performance without restriction.  |
| 1            | Symptoms, but ambulatory. Restricted in physically strenuous activity, but ambulatory and able to carry out work of a light or sedentary nature (e.g., light housework, office work). |
| 2            | In bed <50% of the time. Ambulatory and capable of all self-care, but unable to carry out any work activities. Up and about more than 50% of waking hours.                            |
| 3            | In bed >50% of the time. Capable of only limited self-care, confined to bed or chair more than 50% of waking hours.   |
| 4            | 100% bedridden. Completely disabled. Cannot carry on any self-care. Totally confined to bed or chair.   |
| 5            | Dead.   |

**Karnofsky Performance Scale**

| Percent | Description   |
|----------------|--|
| 100            | Normal, no complaints, no evidence of disease.                                 |
| 90             | Able to carry on normal activity; minor signs or symptoms of disease.          |
| 80             | Normal activity with effort; some signs or symptoms of disease.                |
| 70             | Cares for self, unable to carry on normal activity or to do active work.       |
| 60             | Requires occasional assistance, but is able to care for most of his/her needs. |
| 50             | Requires considerable assistance and frequent medical care.                    |
| 40             | Disabled, requires special care and assistance.                                |
| 30             | Severely disabled, hospitalization indicated. Death not imminent.              |
| 20             | Very sick, hospitalization indicated. Death not imminent.                      |
| 10             | Moribund, fatal processes progressing rapidly.                                 |
| 0              | Dead.  |

## APPENDIX B

### **Instructions for pills**

1. Store at room temperature
2. Keep canisters out of reach of children
3. If you can, take your pills at the same time. If you forget to take it at the same time, take it any time that you remember.
4. If you prefer to take the pills at another time (for example, when you take your other medications) that is OK, as long as you remember to take it daily.
5. Always take the pills after a light meal.
6. If you start any new medications while you are on study, please call your study coordinator. She will check with the study doctor and if needed, with your personal physician so that possible interactions can be managed safely.
7. Avoid fasting or taking vitamin C, fish oil , calcium, magnesium, or milk with the Polyphenon capsules. You should take your Polyphenon E/EGCG capsules with a cup of water after a light meal without milk or juice during the meal. You should not make up the missing dose the next day. You should not make up vomited doses. The missing dose or vomited dose should be reported in the medication diary.

## APPENDIX C

Participant ID \_\_\_\_\_

Study Coordinator Signature:

Date:

**APPENDIX D**  
**Hepatotoxicity Assessment Algorithm**

| Baseline ALT or AST             | Liver toxicities  | Treatment and follow up plan   |
|---------------------------------|---|--|
| Normal                          | ALT or AST increases to $\geq 5$ x upper limit of normal AND no liver related symptoms (nausea, vomiting, right upper quadrant pain)  | Repeat liver profile (AST, ALT, bilirubin (total, direct, and indirect) and INR) within 3 to 4 days. Email NCPC and the protocol PI within 48 hours of learning about the event ( [contact] and [contact] ).   |
| Elevated                        | ALT or AST increases to $\geq 3$ x baseline levels AND no liver related symptoms (nausea, vomiting, right upper quadrant pain)  | Interrupt the study medication. Initiate potential DILI work-up for competing etiologies, repeat liver profile and INR within 48-72 hours. Study medication can be restarted only if a firm competing etiology is identified and liver tests return to baseline. Email NCPC and the protocol PI within 48 hours of learning about the event ( [contact] and [contact] ). |
| Irrespective of baseline levels | ALT or AST increase to $\geq 3$ x baseline AND symptoms of clinical hepatitis (vomiting, nausea, right upper quadrant pain)   | Interrupt the study medication. Initiate potential DILI work-up for competing etiologies, repeat liver profile and INR within 48-72 hours. Study medication can be restarted only if a firm competing etiology is identified and liver tests return to baseline. Email NCPC and the protocol PI within 48 hours of learning about the event ( [contact] and [contact] ). |
| Irrespective of baseline levels | Elevations in direct bilirubin $> 1.5 \times$ ULN, and if ALT or AST $\geq 3$ x baseline but without liver related symptoms (vomiting, nausea, right upper quadrant pain)   | Interrupt the study medication. Initiate potential DILI work-up for competing etiologies, repeat liver profile and INR within 48-72 hours. Study medication can be restarted only if a firm competing etiology is identified and liver tests return to baseline. Email NCPC and the protocol PI within 48 hours of learning about the event ( [contact] and [contact] ). |
| Irrespective of baseline levels | With any elevation of direct bilirubin $>$ ULN, regardless of ALT or AST levels, AND with indicators of immunological reaction (i.e., rash or $> 5\%$ eosinophilia), or appearance of nausea, vomiting, right upper quadrant pain (symptoms consistent with clinical hepatitis) | Permanently discontinue study medication. Initiate potential DILI work-up for competing etiologies, repeat liver profile and INR within 48-72 hours, and place patient under "close observation" as defined in the DILI guidance. Email NCPC and the protocol PI within 48 hours of learning about the event ( [contact] and [contact] ).                                |

Criteria for taking patients off agent:

- 1) If close monitoring of a patient is not possible, or
- 2) Any elevation of direct bilirubin  $>$  ULN, regardless of ALT or AST levels, AND with indicators of immunological reaction (i.e., rash or  $> 5\%$  eosinophilia), or appearance of nausea, vomiting, right upper quadrant pain (symptoms consistent with clinical hepatitis)
- 3) Any development of recurrent hepatotoxicity (as outlined in this table) upon rechallenge.
- 4) Any hepatic decompensation such as
  - New onset ascites or worsening of ascites (requiring increase in drug therapy or requiring surgical intervention such as paracentesis).
  - Variceal bleeding documented by endoscopy
  - Spontaneous bacterial peritonitis documented by positive culture
  - Hepatic encephalopathy
  - Hepatorenal syndrome (Type 1 or 2)
  - Porto-pulmonary hypertension
  - Hepato-pulmonary hypertension
  - Any liver related event that leads to hospitalization or G4 event.

Email NCPC and the protocol PI within 48 hours of learning a participant needs to be taken off agent ([[contact]](mailto:[contact]) and [[contact]](mailto:[contact])).

If a participant meets any of these criteria, email NCPC and the protocol PI within 48 hours of learning about the event ([[contact]](mailto:[contact]) and [[contact]](mailto:[contact])).

1. If direct bilirubin remains in the normal range during the trial and only transaminase elevations are observed:

- When the baseline ALT or AST are normal at baseline and increase to  $\geq 5$ x upper limit of normal (ULN) during the trial **AND** the patient does not have liver related symptoms (nausea, vomiting, right upper quadrant pain) then
  - *Repeat liver profile (AST, ALT, Bilirubin (total, direct, and indirect)) and INR within 3 to 4 days. Monitor the patient as per “close observation” definition in the DILI guidance.*
- When the ALT or AST are elevated at baseline and increase to  $\geq 3$ x baseline during the trial **AND** the patient does not have liver related symptoms (nausea, vomiting, right upper quadrant pain) then
  - *Interrupt the study medication. Initiate potential DILI work-up for competing etiologies, repeat liver profile and INR within 48-72 hours, and place patient under “close observation” as defined in the DILI guidance. Study medication can be restarted only if a firm competing etiology is identified and liver tests return to baseline.*
- When the ALT or AST increase to  $\geq 3$ x baseline (irrespective of baseline levels) during the trial and are associated with symptoms of clinical hepatitis such as vomiting, nausea, right upper quadrant pain), then
  - *Interrupt the study medication. Initiate potential DILI work-up for competing etiologies, repeat liver profile and INR within 48-72 hours, and place patient under “close observation” as defined in the DILI guidance. Study medication can be restarted only if a firm competing etiology is identified and liver tests return to baseline.*

2. For patients with elevations in direct bilirubin  $> 1.5 \times$  ULN, and if ALT or AST  $\geq 3 \times$  baseline but without liver related symptoms (vomiting, nausea, right upper quadrant pain) then

- *Interrupt the study medicine. Initiate potential DILI work-up for competing etiologies, repeat liver profile and INR within 48-72 hours, and closely observe the patient. For “close observation” of patients, refer to the DILI guidance. Study medication can be restarted only if a firm competing etiology is identified and the liver tests return to baseline.*

3. With any elevation of direct bilirubin  $>$  ULN, regardless of ALT or AST levels, and in the presence of indicators of immunological reaction (i.e., rash or  $> 5\%$  eosinophilia), or appearance of nausea, vomiting, right upper quadrant pain (symptoms consistent with clinical hepatitis) then

- *Permanently discontinue study medication. Initiate potential DILI work-up for competing etiologies, repeat liver profile and INR within 48-72 hours, and place patient under “close observation” as defined in the DILI guidance.*

**If a patient lives in a remote area, they can be tested locally and the results communicated to the investigator site promptly.**

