Cirrhotic participants are likely to have a baseline increase in transaminases. We deduce this from the fact that most participants are found to have cirrhosis only after having a blood test for an unrelated condition (such as chronic viral hepatitis, non-alcoholic steatohepatitis, or alcoholic liver disease) that causes elevated transaminases. A mild increase ( $</= 2.5 \times$  upper normal level (UNL)) in transaminase does not reflect the level of liver function impairment in well-compensated cirrhosis. To ensure safety, subjects selected will have normal direct bilirubin, and synthetic function including albumin  $\geq 3.0 \text{ g/dL}$  and INR  $\leq 1.3$ . Following FDA recommendations, weekly or bi-weekly (depending on assigned dose, clinical stability, and liver biochemical stability of the participant) liver function & coagulation tests will be carried out for safety monitoring. We propose to enroll participants with baseline AST/ALT that is less than  $2.5 \times$  UNL. Change of transaminase levels from baseline will be used to monitor the hepatotoxicity of Polyphenon E. In participants who develop changes in transaminases, we will hold treatment until levels recover to baseline OR discontinue therapy based on the extent of the increase of AST/ALT from the baseline level, according to the detailed dose modification/withholding drug scheme for elevated ALT/AST described in Section 5.6.

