The safety of tea and tea compounds is supported by centuries of human consumption. However, in recent years, oral use of green tea extracts (GTEs) has been associated with several instances of hepatotoxicity [67, 68]. Most affected participants were women, and many were consuming GTEs for the purpose of weight loss. Although hepatotoxicity in most cases resolved within four months of stopping GTE, there have been cases of positive rechallenge and liver failure requiring liver transplantation. A written safety report submitted to NCI, DCP-sponsored IND [REDACTED] in December 2005 described a case of acute liver failure in a woman consuming Green Lite® capsules distributed by Origin Biomedicinals, Inc., Halifax, Canada. Green Lite capsules contain Polyphenon 70A, a GTE manufactured by Mitsui Norin, and similar in composition to Polyphenon E. In addition, the sale of Exolise (an ethanolic GTE sold as a weight reduction aid) was suspended in Spain in 2003 after reports of hepatotoxicity (four cases in Spain and nine in France) associated with its use [69]. Time to onset of hepatotoxicity following ingestion of GTEs ranged from several days to several months. Increased oral bioavailability occurs when GTEs are administered on an empty stomach after an overnight fast. These severe adverse reactions appear to be rare and have never been reported in any subject administered Polyphenon E. However, increased toxicity, including hepatotoxicity, is observed when Polyphenon E or EGCG is administered to fasted dogs. Therefore, the FDA Division of Oncology Products has recommended that Polyphenon E be taken with food by subjects participating in clinical studies. In addition, subjects should have liver function tests performed at baseline and repeated every four weeks while on treatment. Following any elevation in ALT, study drug should be withheld (grade 1) or discontinued (grade  $\geq 2$ ), and liver function monitored until recovery to normal.

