- h. In between Visits 1 and 2, and between Visits 2 and 3, liver function & coagulation tests including AST, ALT, alkaline phosphatase, total protein, albumin, direct bilirubin, indirect bilirubin, total bilirubin, magnesium, GGT, calcium, phosphorus, and INR will be performed according to the schedule below. These tests will be performed at the central lab, or, if the participant prefers, at a local clinic lab. Participants who experience hepatotoxicity according to Appendix D will be re-evaluated every 3-4 days until resolution.
  - a. For participants assigned to 400 mg EGCG QD or 400 mg EGCG BID: bi-weekly liver function & coagulation testing (every 14 +/- 3 days).
  - b. For participant assigned to  $\geq$ 600 mg EGCG BID: weekly liver function & coagulation testing (every 7 +/- 3 days) for the first 2 weeks on agent, or until the participant demonstrates stability of clinical condition and liver biochemical enzymes\* for at least 2 weeks, whichever is longer. Thereafter, the participant will receive bi-weekly liver function & coagulation testing (every 14 +/- 3 days).

\*Stability of clinical condition and liver biochemical enzymes is defined as meeting all of the following, as listed in Appendix D:

- a. No symptoms of clinical hepatitis (vomiting, nausea, right upper quadrant pain)
- b. No ALT or AST increases to  $\geq$ 5x upper limit of normal
- c. No ALT or AST increases to  $\geq$ 3x baseline levels
- d. No elevations in direct bilirubin  $>$  1.5 ULN
- e. No elevation of direct bilirubin  $>$  ULN, regardless of ALT or AST levels, with indicators of immunological reaction (i.e., rash or  $>$ 5% eosinophilia).

- i. For details on the Child-Pugh score, see [https://www.qxmd.com/calculate/calculator\\_43/child-pugh-score](https://www.qxmd.com/calculate/calculator_43/child-pugh-score).
- j. Only the subjects with  $\gamma$ -OHPdG-high in the base-line liver biopsy will be registered for treatment. The treatment is to start within 14 days from registration. The subjects with  $\gamma$ -OHPdG-low liver

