#### **Close observation:**

1. Interrupt the investigational agent administration
2. Repeat liver biochemistries and additional testing within 24-72 hrs

 (refer to the “Guidance for Industry : Drug induced liver injury (DILI): Premarketing clinical evaluation” <http://www.fda.gov/downloads/Drugs/.../Guidances/UCM174090.pdf>)

3. Monitor patient twice or thrice a week until liver biochemistries (ALT, AST, alkaline phosphatase, bilirubin (total, direct, and indirect), and coagulation profile [INR]) resolve, stabilize or return to within baseline values
4. Monitor liver biochemistries once a week if abnormalities stabilize and the patient is asymptomatic
5. Obtain a detail history for symptoms assessment: appearance or worsening of clinical symptoms of hepatitis (fatigue, nausea, vomiting, right upper quadrant pain or tenderness, fever, rash or eosinophilia). If a patient is symptomatic, the drug must be discontinued immediately and a potential DILI evaluation must be performed.
6. Obtain a more detailed history of symptoms and prior or concomitant diseases;
7. Obtain a history for concomitant medications, acetaminophen, dietary supplements, herbal remedies, other over the counter medications, recreational drug use, and special diets
8. If possible quantify the alcohol consumption to assess for alcoholic hepatitis
9. Obtain a history of exposure to environmental chemical agents.
10. If INR is also elevated, a trial of intravenous vitamin K administration may be considered, especially in cholestatic patients.

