**Follow-Up Procedures for patient(s) who meet *potential DILI evaluation criteria*:**

1. Viral hepatitis serology including:
  - a. Hepatitis A IgM antibody;
  - b. Hepatitis B surface antigen and Hepatitis B Core Antibody (IgM);
  - c. Hepatitis C RNA;
  - d. Hepatitis E IgM antibody.
  - e. Cytomegalovirus IgM antibody;
  - f. Epstein-Barr viral capsid antigen IgM antibody (or if unavailable, obtain heterophile antibody or monospot testing); however IgM antibodies must be sent out asap
  - g. Blood sample for pharmacokinetic (PK) analysis, obtained within 12 hours of last dose. Record the date/time of the PK blood sample draw and the date/time of the last dose of study treatment prior to blood sample draw on the CRF. If the date or time of the last dose is unclear, provide the participant's best approximation.
  - h. Serum creatine phosphokinase (CPK) and lactate dehydrogenase (LDH).
  - i. Fractionate bilirubin, if total bilirubin  $>2\times$ ULN
  - j. Assess for peripheral eosinophilia
  - k. Assess for hypoxic/ischemic hepatopathy; and biliary tract disease

The following are required for patients who meet the stopping criteria for both ALT and bilirubin OR experiences clinical symptoms of hepatitis:

1. Anti-nuclear antibody, anti-smooth muscle antibody, Type 1 anti-liver kidney microsomal antibodies and quantitative total immunoglobulin G (IgG or gamma globulins).
2. If required evaluation of competing undiagnosed liver disease (hemochromatosis, Wilson's disease, alpha-1 anti-trypsin deficiency)
3. Serum acetaminophen levels OR serum acetaminophen adducts by HPLC assay (quantifies potential acetaminophen contribution to liver injury in participants with definite or likely acetaminophen use in the preceding week).
4. Liver imaging (ultrasound, magnetic resonance, or computerized tomography) to evaluate liver disease.
5. A Liver Biopsy

Treatment with investigational agent could be re-initiated if these abnormalities stabilize, return to pre-trial baseline, or normalize.

Investigational agent must be permanently discontinued and patient must be followed until the clinical and laboratory abnormalities stabilize or normalize if the following criteria are met:

- 1) If close monitoring of a patient is not possible. or

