- 2) Any elevation of direct bilirubin > ULN, regardless of ALT or AST levels, AND with indicators of immunological reaction (i.e., rash or >5% eosinophilia), or appearance of nausea, vomiting, right upper quadrant pain (symptoms consistent with clinical hepatitis)
- 3) Any development of recurrent hepatotoxicity (as outlined in this table) upon rechallenge.
- 4) Any hepatic decompensation as
  - New onset ascites or worsening of ascites (requiring increase in drug therapy or requiring surgical intervention such as paracentesis).
  - Variceal bleeding documented by endoscopy
  - Spontaneous bacterial peritonitis documented by positive culture
  - Hepatic encephalopathy
  - Hepatorenal syndrome (Type 1 or 2)
  - Porto-pulmonary hypertension
  - Hepato-pulmonary hypertension
  - Any liver related event that leads to hospitalization or G4 event.

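### Appendix D gives two incompatible restart rules after ALT or AST reaches three times baseline

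*Combined protocol and SAP*

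**What the plan says.** The Appendix D table has five rows. Three of them are triggered by ALT or AST of at least 3x baseline:

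- elevated baseline, no symptoms;
- any baseline, with symptoms of hepatitis;
- any baseline, with direct bilirubin above 1.5x ULN and no symptoms.

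Each of the three orders interruption and a potential DILI work-up, and then states: "Study medication can be restarted only if a firm competing etiology is identified and liver tests return to baseline". The numbered instructions below the table repeat both conditions for the same three situations. The normal-baseline row (at least 5x ULN, no symptoms) has no restart condition. The fifth row orders a permanent stop.

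Under Follow-Up Procedures for participants who meet the potential DILI evaluation criteria, after the lists of tests, Appendix D says: "Treatment with investigational agent could be re-initiated if these abnormalities stabilize, return to pre-trial baseline, or normalize". The list of permanent-discontinuation criteria follows, including "Any development of recurrent hepatotoxicity (as outlined in this table) upon rechallenge".

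Between these two parts, Close observation item 4 says "Monitor liver biochemistries once a week if abnormalities stabilize and the patient is asymptomatic" and item 5 says "If a patient is symptomatic, the drug must be discontinued immediately and a potential DILI evaluation must be performed".

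Outside the appendix, Section 2.5.2 says "we will hold treatment until levels recover to baseline OR discontinue therapy based on the extent of the increase of AST/ALT". Section 6.2 reports an FDA recommendation: "Following any elevation in ALT, study drug should be withheld (grade 1) or discontinued" for higher grades. Sections 5.6 and 8.3 send the reader back to Appendix D.

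**The concern.** A participant whose ALT triples, who has no symptoms, and in whom no other cause is found may not be restarted under the table. Under the follow-up sentence the same participant may be restarted once the values level off, even well above baseline.

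The stakes are about rechallenge safety. Everyone treated has cirrhosis. Section 6.2 reports positive rechallenge and liver failure leading to transplantation with green tea extracts, although it adds that such severe reactions had not been reported with Polyphenon E. The restart rule in a hepatotoxicity algorithm should therefore have one meaning.

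**Working it through.** There is no stated figure to reproduce, so the check is a comparison of the texts.

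**1. Do both rules reach the same people?** Yes. Each of the three at-least-3x-baseline rows orders a potential DILI work-up, and the follow-up section is headed for participants in that evaluation.

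**2. Do the conditions differ?**

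| | Table and numbered instructions | Follow-up section |
|---|---|---|
| Alternative cause required | Yes | No |
| Liver tests | Back to baseline | Stable, or back to baseline, or normal |
| Logic | Both conditions | Any one of three |
| Times written | 3 rows + 3 instructions = 6 | 1 |

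**3. Could stabilizing mean returning to baseline?** No. "Treatment with investigational agent could be re-initiated if these abnormalities stabilize, return to pre-trial baseline, or normalize" lists them as separate alternatives, and Close observation item 3 separates them too. Item 4 ("Monitor liver biochemistries once a week if abnormalities stabilize and the patient is asymptomatic") keeps weekly monitoring going after stabilization, which treats the values as still abnormal.

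**4. Does another section settle it?** No.
- Section 2.5.2 asks for recovery to baseline but has no cause condition. It points to Section 5.6, which points back to Appendix D.
- Section 6.2 covers withholding and stopping and gives no restart rule.
- Section 8.5 places the study on hold once 4 or more participants meet an Appendix D criterion, but does not govern an individual restart.

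**5. How far apart are the permitted restart levels?** Write b for the baseline as a multiple of ULN. Table 2 in Section 4.1 caps entry at 2.5x. The table requires a return to b; the follow-up sentence gives no ceiling.

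As an illustration only, assume that stabilizing takes the one stability definition in the protocol (Section 7.1, footnote h: "Stability of clinical condition and liver biochemical enzymes is defined as meeting all of the following, as listed in Appendix D"), meaning no value at or above 3x baseline or 5x ULN. Section 7.1 uses that definition to set testing frequency, not to permit restart. The ceiling would be just below min(3b, 5) x ULN:

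| b | Ceiling (x ULN) | Ratio to b |
|---|---|---|
| 1.25 | 3.75 | 3.0 |
| 1.5 | 4.5 | 3.0 |
| 2.0 | 5.0 | 2.5 |
| 2.5 | 5.0 | 2.0 |

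**6. What must the repair leave alone?** The normal-baseline row needs a restart rule. Section 5.6 holds drug for any liver-test elevation, and the numbered instruction for that row invokes close observation, whose item 1 interrupts dosing. The follow-up sentence is the only restart rule in Appendix D that can reach it. Such a participant has b of at most 1.0, so 5x ULN is at least 5/1.0 = 5 times baseline. A repair worded only as at least 3x baseline would capture this row by accident, so it has to name the rows.

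**The case against.** **The strict wording already controls.** The best defence is that the table is specific and says only if, while the follow-up sentence is general and says could be. Read that way, the sentence serves the normal-baseline row and the table governs the rest. This is the sensible reading and it shapes the fix, but the appendix does not state it, and the general sentence sits under the heading that the three rows lead to.

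**Oversight limits the risk.** Each row requires an email to the consortium and the protocol PI within 48 hours. That makes an unnoticed restart less likely, but it is notification, not approval.

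**A stronger reading of the symptomatic row.** A reader might infer that item 5 ("If a patient is symptomatic, the drug must be discontinued immediately and a potential DILI evaluation must be performed") contradicts the restart path for symptomatic participants. The documents do not establish this. Where Appendix D means a final stop it writes permanently; item 5 does not, and it pairs the stop with performing the evaluation. It can mean that dosing stops pending the work-up, which agrees with the row.

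**A stronger reading of the Discontinue Therapy Criteria (DTC).** A reader might infer that DTC counts are unreliable. An asymptomatic participant who can never be restarted is not named in the permanent-discontinuation lists, and the recurrence criterion presupposes a rechallenge. But those lists can be read as the whole content of DTC limb (b), and Section 8.3 names interruption and permanent discontinuation as separate actions. Related events of grade 3 or higher and hepatic decompensation are DTCs under limbs (a) and (c) anyway. The text leaves a clarification to make, and no miscount is shown.

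**Conclusion.** The restart rules conflict as written for the three at-least-3x-baseline situations, and the text supplies no precedence. This conclusion rests on wording alone. The 2.0- to 3.0-fold range in the working depends on a borrowed definition and only indicates what the permissive wording could allow.

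Severity is minor. Sections 8.1 and 13.1 say that enrollment stopped early, that 13 participants started and that no MTD can be established. No interruptions are reported, and nobody is identified as still on agent. The documents do not support the inference that Table 6 would change or that the suggestion of dose level 3 for future studies is undermined.

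Classification of a non-liftable interruption could matter if the algorithm is reused. The chance that a dose passes 3+3 is (1-p)^3 + 3p(1-p)^5. With an assumed 10% rate of clear DTCs it is 0.729 + 0.177 = 0.906. If a further assumed 10% of non-liftable interruptions also counted (p = 0.20), it is 0.512 + 0.197 = 0.709. Both rates are invented for illustration; the documents give none.

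**What to change.** Amend the re-initiation sentence in the Follow-Up Procedures part of Appendix D. For participants who met the elevated-baseline, symptomatic, or direct-bilirubin row at 3x baseline or more, restart is allowed only when a firm alternative cause has been found and liver tests are back at baseline. The sentence as it stands continues to apply to the normal-baseline row (at least 5x ULN, no symptoms).

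Keep the symptomatic row's restart path. At most, add to Close observation item 5 that dosing stops pending the work-up unless a permanent-discontinuation criterion is met.

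Optionally, state in the DTC definition (Sections 3.1 and 8.3) whether an asymptomatic interruption that cannot be lifted counts under limb (b), and by when that is decided relative to the four-week window. Without a decision time, an interruption whose work-up is still pending at week 4 stays unclassified.

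The cost is one sentence, plus up to two clarifications, with no new visits, tests or data. Participants with stable but unexplained elevations would stay off drug, as the table already requires.
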